### **3.5.1.1. Adverse events of interest**

The TEAEs of interest for additional reporting are: nausea, vomiting and diarrhoea (as defined based on preferred term). Based on emerging blinded data reviews, other AEs of interest may be added to this list, which would be documented with a SAP amendment or documented in the changes to planned analysis section in the CSR.

### **3.5.1.2. Subset reporting interval**

A subset reporting interval of the TEAEs of interest (as defined in Section 3.5.1.1) will be defined by a shorter reporting interval than that defined for the main reporting interval. This interval will include adverse events of interest (reported separately) if:

- the event starts after or on the first dose, but doesn't start more than two days after the last dose of IP (defined as either completing the 12 weeks of treatment or discontinuing from IP earlier).

CCI

### **3.5.2. Hypoglycemic Monitoring**

Hypoglycemia AEs will be recorded in the AE Case Report Form (CRF) with details of the event captured on the Hypoglycemic Event Details CRF. Details of when these will be recorded are given in the protocol (Section 8.2.4.2).

For programming purposes, the hypoglycemic AE categories are based on the following:

- Severe Hypoglycemia: Severe is checked in the severity criteria of the CRF. This assessment will be made by the PI based on the protocol definition.
- Documented Symptomatic Hypoglycemia: If (2 – Did the participant have symptoms of hypoglycemia?) Yes and (3 – Was the blood glucose measured?) Yes and result

<70 mg/dL (or <3.9 mmol/L) on the CRF, but hypoglycemia is not classified as severe.

- Asymptomatic Hypoglycemia: If (2) No and (3) Yes and result <70 mg/dL (or <3.9 mmol/L) on the CRF, but hypoglycemia is not classified as severe.
- Probable Symptomatic Hypoglycemia: If (2) Yes and (3) No and (3a – If blood glucose was not measured, did symptoms resolve when treated with carbohydrate or glucagon?) Yes on the CRF, but hypoglycemia is not classified as severe.

### **3.5.3. Laboratory Data**

Safety laboratory tests (hematology, chemistry, urine testing and other clinical laboratory tests) will be performed as described in the protocol.

To determine if there are any clinically significant laboratory abnormalities, the safety tests will be assessed against the criteria specified in the sponsor reporting standards. The assessment will take into account whether each participant's baseline test result is within or outside the laboratory reference range for the particular laboratory parameter.

Baseline for all laboratory measurements will be defined as the result closest prior to dosing at Visit 3 (Day 1).

#### **3.5.3.1. Change from Baseline Summaries**

Focused change from baseline summaries of the following safety laboratory endpoints will be assessed:

- Change from baseline in calcitonin to all post-dose time points as per the Schedule of Activities (SOA)
- Change from baseline in amylase to all post-dose time points as per the SOA
- Change from baseline in lipase to all post-dose time points as per the SOA
- Change from baseline in thyroid stimulating hormone (TSH) to all post-dose time points as per the SOA
- Change from baseline in free thyroxine (free T4) to all post-dose time points as per the SOA
- Change from baseline in lipid profile (total cholesterol, direct LDL cholesterol, HDL cholesterol and triglycerides) to all post-dose time points as per the SOA
- Change from baseline in liver function tests (ALT, AST, alkaline phosphatase, total bilirubin, bile acids and gamma-glutamyl transferase [GGT]) to all post-dose time points as per the SOA

- Change from baseline in estimated glomerular filtration rate (eGFR) to all post-dose time points as per the SOA

### 3.5.3.2. Clinical Laboratory Parameters of Interest

For the specific laboratory parameters listed in the table below, the following endpoints will be derived:

- Abnormalities defined as either a “Flag Level” or “Alert Level” as in the table below

Parameter	Flag Level	Alert Level	Conventional Units
Fasting Plasma Glucose	< 70 ≥ 270	≤ 54 ≥ 270	mg/dL
Amylase	>ULN	Pfizer standard flag for PCC	U/L
Lipase	>ULN	Pfizer standard flag for PCC	U/L
Calcitonin	>ULN	Pfizer standard flag for PCC	pg/mL
Alanine Aminotransferase	≥ 2 ULN	Pfizer standard flag for PCC	U/L
Aspartate Aminotransferase	≥ 2 ULN	Pfizer standard flag for PCC	U/L
Alkaline Phosphatase	≥ 2 ULN	Pfizer standard flag for PCC	U/L
Gamma Glutamyl Transferase	≥ ULN	Pfizer standard flag for PCC	U/L
Total Bilirubin	> 1.5 ULN	Pfizer standard flag for PCC	mg/dL
Serum Total Bile Acids	>ULN	Pfizer standard flag for PCC	μmol/L

PCC – potential clinical concern

ULN – upper limit of normal as determined by the central laboratory

These endpoints will be derived using both pre and post-dose data separately. Post-dose will include all post-baseline data including unplanned readings and pre-dose will include all data from the placebo run-in defined by including all values from Visit 2 to pre-dose, including the baseline measurement and unplanned readings. Note, both pre- and post-dose populations will be from the safety analysis set (defined in Section 4).

### 3.5.4. Vital Signs

Vital sign measurements (systolic blood pressure, diastolic blood pressure and pulse rate) will be taken as detailed in the Schedule of Activities given in the protocol. The average of the triplicate measurements collected at each appropriate assessment time will be calculated for each vital sign parameter.

Baseline will be defined as the result closest prior to dosing at Visit 3 (Day 1), where “result” refers to the average of a triplicate measurement.

Changes from baseline for supine systolic and diastolic blood pressure and pulse rate will be calculated for each post baseline measurement.

### **3.5.5. Electrocardiograms (ECGs)**

Standard 12-lead ECG (including heart rate, QT, QTcF, PR and QRS interval) will be obtained at times detailed in the Schedule of Activities given in the protocol. The average of the triplicate readings collected at each appropriate assessment time will be calculated for each ECG parameter.

For reporting, QTcF will be derived based on the CRF entered heart rate and QT interval values as:

$$QTcF = \frac{QT \text{ Interval}}{\sqrt[3]{\frac{60}{\text{heart rate}}}}$$

Where QT interval is in msec and heart rate is in beats/min. The CRF entered QTcF will therefore not be included in any analysis or reported in CSR tables.

Baseline will be defined as the result closest prior to dosing at Visit 3 (Day 1), where “result” refers to the average of a triplicate measurement.

Change from baseline for heart rate, QT, QTcF, PR and QRS interval will be calculated for each post baseline measurement.

### **3.5.6. Assessment of Mental Health**

- Assessment of mental health as determined by Columbia-Suicide Severity Rating Scale (C-SSRS) and Patient Health Questionnaire-9 (PHQ-9).

The C-SSRS is a validated tool to evaluate suicidal ideation and behaviour. Data relevant to the assessment of suicidality will be mapped to the Columbia-Classification Algorithm of Suicide Assessment (C-CASA) codes as given in Appendix 6).

For this endpoint the screening visit will be labelled as ‘Lifetime’ in tables and the recent history (i.e. past 12 months) will also be reported separately.

*The PHQ-9 is a 9 item self-report scale for the assessment of depressive symptoms. The PHQ-9 will be completed by participants and reviewed by site staff at the pre-defined time points outlined in the SOA.*

The PHQ-9 total score will be derived for each time point separately by summing the responses to the 9 questions. Baseline is defined as the last pre-dose measurement.

## 4. ANALYSIS SETS (POPULATIONS FOR ANALYSIS)

Data for all participants will be assessed to determine if participants meet the criteria for inclusion in each analysis population prior to unblinding and releasing the database and classifications will be documented per standard operating procedures.

Population	Description
Enrolled	All participants who sign the ICD.
Randomly assigned to IP	All participants randomly assigned to IP regardless of whether or not IP was administered.
Evaluable	All participants randomly assigned to IP and who take at least 1 dose of IP. Participants will be analyzed according to the randomized intervention.
Safety	All participants randomly assigned to IP and who take at least 1 dose of IP. Participants will be analyzed according to the product they actually received.

Defined Population for Analysis	Description
Estimand Set 1A (related to estimands 1A, 2A & 3A)	All evaluable participants with T2DM randomly assigned to IP and who take at least 1 dose of IP. For participants who discontinue IP and/or receive glycemic rescue medication, all subsequent values will be censored.
Estimand Set 1B (related to estimands 1B, 2B & 3B)	All evaluable non-diabetic participants with obesity randomly assigned to IP and who take at least 1 dose of IP. For participants who discontinue IP, all subsequent values will be censored.
PK Concentration Set	All participants randomly assigned to IP and who take at least 1 dose of PF-06882961 and in whom at least 1 concentration value is reported.

### 4.1. Strata Misallocations

Participants who are randomized to the wrong stratum, in error, will have the incorrect stratum assignment remain in IMPALA but the clinical database will include the correct stratum. The latter will subsequently be used for all relevant analyses.

## 5. GENERAL METHODOLOGY AND CONVENTIONS

### 5.1. Hypotheses and Decision Rules

Exploratory statistical analysis will be performed on the primary endpoint related to AEs of interest only (as defined in Section 3.5.1.1). For this analysis, the null hypothesis is that there

is no difference between treatment groups. The alternative hypothesis is that there is a difference between treatment groups. Note this will be applied to testing the difference between 2 separate treatment groups (rather than testing for differences across all treatment groups). The Type I error rate ( $\alpha$ -level) used for the statistical inference will be 5% (2-sided).

Statistical analysis will also be performed on the secondary endpoints related to Estimands: 1A and 1B related to change from baseline in FPG; 2A and 2B related to change from baseline in HbA1c; and 3A and 3B related to change from baseline in body weight. For these estimands, the null hypothesis is that there is no difference between PF-06882961 and placebo on the secondary endpoints. The alternative hypothesis is that PF-06882961 is superior (i.e. greater reduction) to placebo on the secondary endpoints. The Type I error rate ( $\alpha$ -level) used for the statistical inference will be 5% (1-sided). Each dose of PF-06882961 will be tested separately compared to placebo.

No adjustment for multiple comparisons will be made for any of the analyses described above, as the primary objective of this study is summarizing tolerability.

## 5.2. General Methods

The analyses related to the primary, secondary and exploratory endpoints will be based on the appropriate population for analysis (see Section 4).

Unless otherwise stated, all summaries and plots will be presented by treatment group. The following treatment group labels (or similar) will be used:

Arm	Strata	Treatment group label
5	T2DM	Placebo (T2DM)
5	Non-diabetic obesity	Placebo (non-diabetic obesity)
3	T2DM	PF-06882961 80 mg BID low, slow (T2DM)
4	T2DM	PF-06882961 80 mg BID high, slow (T2DM)
1	T2DM	PF-06882961 120 mg BID low, fast (T2DM)
2	T2DM	PF-06882961 120 mg BID high, fast (T2DM)
6	T2DM	PF-06882961 200mg BID (T2DM)
7	Non-diabetic obesity	PF-06882961 200mg BID (non-diabetic obesity)

### 5.2.1. Analyses for Continuous Endpoints

Continuous variables will be presented using summary statistics: number of observations, arithmetic mean, standard deviation, median, minimum and maximum values.

### 5.2.2. Analyses for Categorical Endpoints

Categorical variables will be presented using summary statistics: number of observations, counts and percentages.

### 5.2.3. Mixed Model Repeated Measures (MMRM)

The mixed model repeated measures (MMRM) *model will include treatment, time, strata (male versus female) and treatment-by-time interaction as fixed effects, baseline as a covariate and the baseline-by-time interaction with time fitted as a repeated effect and*

*participant as a random effect.* The baseline covariate will be based on the associated endpoint being analysed (i.e. for Estimands 1, 2 and 3, baseline FPG, HbA1c and body weight will be used, respectively).

An unstructured covariance matrix will be used to estimate the variances and covariance within participant across time points. If convergence is not obtained or model fit is not adequate, then other covariance structures will be investigated as necessary. The Kenward-Roger approximation will be used for estimating degrees of freedom for the model parameters.

Missing values (e.g. due to censoring) will be implicitly imputed as part of the MMRM model fitting.

The Least Squares Means (LSMeans) together with 90% confidence intervals, standard errors and p-values (2-sided) will be obtained for each treatment group at each time point.

Differences in LSMeans between each treatment group of PF-06882961 relative to placebo (from the same population) at each time point, together with 90% confidence intervals, standard errors and p-values (1-sided, unless otherwise stated), will also be obtained.

Example SAS code is provided in Appendix 2.

#### **5.2.4. Cumulative Incidence Plots**

Cumulative Incidence Plots will be produced based on the time to the event of interest (starting from the time of start of dosing on Day 1) for each treatment group separately and will be plotted on the same graph. This will be based on plotting the cumulative incidence function (with no competing risks), which will be presented as a % on the y-axis. No statistical testing for differences between treatment groups will be considered.

Details of censoring are included in Sections 6.5.6, 6.1.1.2.6 and 6.1.1.2.7 and example SAS code is provided in Appendix 2.

#### **5.3. Methods to Manage Missing Data**

For applicable continuous endpoints modelled with an MMRM, missing/censored values will be imputed as part of the analysis method.

In all PK data presentations (except listings), concentrations below the limit of quantification (BLQ) will be set to zero. In listings BLQ values will be reported as “<LLQ”, where LLQ will be replaced with the value for the lower limit of quantification (LLQ).

### **6. ANALYSES AND SUMMARIES**

Data collected before baseline will only be listed, unless otherwise stated.

For all relevant analyses, treatment arm 5 (the placebo arm) will be presented as two separate treatment groups for the T2DM participants and non-diabetic participants with obesity.

## 6.1. Primary Endpoint(s)

### 6.1.1. Incidence and severity of treatment emergent AEs

#### 6.1.1.1. Main Analysis

Adverse events will be summarized by treatment group and overall and in accordance with sponsor reporting standards using the safety analysis set as defined in Section 4.

Incidence and severity of treatment emergent adverse event (TEAE) tables will additionally be produced ('All causality' and 'Treatment related', separately) to summarize the total number of adverse events by preferred term, which will be reported by treatment group and overall in accordance with sponsor reporting standards using the safety analysis set defined in Section 4.

The adverse events (AEs) will be presented sorted in descending frequency based on the overall number of AEs (by preferred term or system order class as appropriate) across all the treatment groups.

#### 6.1.1.2. Sensitivity/Supplementary Analyses

The following exploratory safety analyses will be restricted to the TEAEs of interest (as defined in Section 3.5.1.1). All sets of outputs in this section would be produced separately for "all causality" TEAEs only.

##### 6.1.1.2.1. Forest plots on the Incidence of adverse events of interest

Forest plots displaying the incidence of TEAEs of interest ("All Causality" only) by treatment group will be produced separately by AE. Each forest plot will present all treatment groups separately (including the placebo groups) and will include 95% confidence intervals (calculated using the Blyth-Still-Casella method[2]).

##### 6.1.1.2.2. Risk differences for adverse events of interest

TEAEs of interest will be tabulated by treatment group, where the number of participants and percent will be presented, along with the risk difference between various treatment comparisons. These will be triaged according to the table below which aim to address different objectives as follows:

Triage Group 1: comparing treatment groups of PF-06882961 in T2DM

Triage Group 2: comparing treatment groups of PF-06882961 in T2DM versus non-diabetic obesity

Triage Group 3: comparing treatment groups for PF-06882961 versus placebo

Triage Group 4: other comparisons

Triage Group	Comparisons
1	PF-06882961 120 mg BID high, fast (T2DM) vs. PF-06882961 120 mg BID low, fast (T2DM) PF-06882961 80 mg BID high, slow (T2DM) vs. PF-06882961 80 mg BID low, slow (T2DM) PF-06882961 120 mg BID low, fast (T2DM) vs. PF-06882961 80 mg BID low, slow (T2DM) PF-06882961 120 mg BID high, fast (T2DM) vs. PF-06882961 80 mg BID high, slow (T2DM)

2	PF-06882961 120 mg BID high, fast (T2DM) vs. PF-06882961 200mg BID (non-diabetic obesity) PF-06882961 200mg BID (T2DM) vs. PF-06882961 200mg BID (non-diabetic obesity)
3	PF-06882961 80 mg BID low, slow (T2DM) vs. Placebo (T2DM)
	PF-06882961 80 mg BID high, slow (T2DM) vs. Placebo (T2DM)
	PF-06882961 120 mg BID low, fast (T2DM) vs. Placebo (T2DM)
	PF-06882961 120 mg BID high, fast (T2DM) vs. Placebo (T2DM)
	PF-06882961 200mg BID (T2DM) vs. Placebo (T2DM)
4	PF-06882961 200mg BID (non-diabetic obesity) vs. Placebo (non-diabetic obesity)
	PF-06882961 120 mg BID low, fast (T2DM) vs. PF-06882961 80 mg BID high, slow (T2DM)
	PF-06882961 120 mg BID high, fast (T2DM) vs. PF-06882961 80 mg BID low, slow (T2DM)
	Placebo (T2DM) vs. Placebo (non-diabetic obesity)

95% confidence intervals will also be presented for the comparison. No adjustment for multiplicity will be used.

TEAEs of interest will also be presented graphically based on the tabular information from above. The TEAEs will be presented in a two-panel plot, the left panel will give the proportions of TEAEs observed in a treatment group of PF-06882961 and separately the other treatment group of comparison (either another treatment group of PF-06882961 or placebo) while the right panel will display the 95% confidence interval for the risk differences for each TEAE. A vertical line corresponding to the value of 0 will be added to the right-hand plot. Each panel will be paged by treatment group of PF-06882961 and the comparison group.

For the above outputs, footnotes will be included on the tables to provide proper interpretation of confidence intervals and to describe how the comparison was conducted, e.g. “Confidence intervals are not adjusted for multiplicity. 95% Confidence intervals are provided to help gauge the precision of the estimates for Risk Difference.”

#### 6.1.1.2.3. Individual profile plot of adverse events of interest over time

A set of individual profile plots will be produced separately for each TEAE of interest. Each plot will include horizontal bars by participant which will represent if/when a participant experienced the TEAE of interest (measured in days). The x-axis will represent time (up to and including the Week 13-14 visit [V10]) and the bars will be coloured by severity, with the plots paged by treatment group. Multiple events for the same participant of the same TEAE would therefore be represented by multiple horizontal bars.

#### 6.1.1.2.4. Incidence of first occurrence of adverse events of interest by week

The number and percentage of participants who experience the first occurrence of a TEAE of interest each week (up to and including Week 12) will be tabulated by treatment group and overall and week, where percentage will be defined in two ways. These will be included in the same table and produced separately for each TEAE of interest.

To calculate the percentage each week, the numerator will be the total number of participants with the TEAE of interest that was also their first post-dose occurrence of the event during that respective week. The two approaches for the denominator are: (1) the total overall number of evaluable participants for the respective treatment group; and (2) the total number

of participants who had not discontinued from IP and/or the study for the respective treatment group prior to that respective week (note if a participant did discontinue from IP and/or the study during that respective week they would be included in the denominator).

A figure of the percentage per week will also be produced, with week on the x-axis and a separate line for each treatment group. The percentage will represent the above definition (2) of the denominator but based on blinded data reviews this figure may be adapted or additionally produced based on definition (1). These figures will be produced separately for each TEAE of interest.

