### 6.1.1. Administration

All doses will be blinded and consist of 3 to 4 tablets administered BID via a blister pack.

Four (4) tablets BID will be administered during the 2-week single-blind placebo run-in and after randomization, during Weeks 1, 2 and 9 of dosing. Three (3) tablets will be administered BID during Weeks 3 to 8 and weeks 10 to 12 of dosing. Single-blinded blister cards will be used for the placebo run-in period. The dosing regimens after randomization will look the same across arms for each dosing window. Blister cards will look the same across all study arms and will contain the same number of tablets for the same time point in treatment.

After randomization during Weeks 1, 2 and 9 of dosing, participants will take 4 tablets of IP (PF-06882961 or matching placebo) in the morning with food and 4 tablets of IP in the evening with food, approximately 10 to 12 hours apart and at approximately the same time each day. Participants will take a total of 8 tablets of IP daily. The same dosing paradigm will be used during the single-blind placebo run-in period.

During Weeks 3 to 8 and Weeks 10 to 12 of dosing, participants will take 3 tablets of IP (in the morning with food and 3 tablets of IP with the evening with food approximately 10 to 12 hours apart and at approximately the same time each day. Participants will take a total of 6 tablets of IP (PF-06882961 or matching placebo) daily.

Participants will swallow the IP whole, and will not manipulate or chew the IP prior to swallowing. To maximize tolerability of PF-06882961 dose will be titrated over a period of 6 to 10 weeks.

The actual titration schemes for PF-06882961 to be used in this study are provided in Table 2 below. The regimen for Arm 5 (the placebo arm) will be placebo tablets administered BID with food in the morning and evening. Arms 1 to 7 are also depicted in [Figure 1](#).

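### The weekly first-occurrence percentage for nausea, vomiting and diarrhoea keeps participants who have already had the event in its denominator, so the plotted line falls in expectation even when the risk of a first event is constant

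*SAP*

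**What the plan says.** The events concerned are "nausea, vomiting and diarrhoea (as defined based on preferred term") (SAP 3.5.1.1). For each of them, SAP 6.1.1.2.4 tabulates by arm and week the participants with a "first occurrence of a TEAE of interest each week (up to and including Week 12").

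The numerator is the "total number of participants with the TEAE of interest that was also their first post-dose occurrence of the event during that respective week". Two denominators appear in the same table:

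- Definition (1) is fixed over time: "The two approaches for the denominator are: (1) the total overall number of evaluable participants for the respective treatment group".
- Definition (2) is the number "of participants who had not discontinued from IP and/or the study for the respective treatment group prior to that respective week".

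For the figure, with one line per arm, the SAP states: "The percentage will represent the above definition (2) of the denominator". After blinded data review the figure may be switched to definition (1), or a second figure based on (1) may be added. No interpretive footnote is planned for this output.

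**The concern.** Once a participant has had the event, he or she can never again satisfy the condition "that was also their first post-dose occurrence of the event during that respective week". Neither denominator removes such participants. Under definition (1) this does no harm if the value is read as what it is, the share of the arm whose first event fell in that week; the weekly values add up to the crude cumulative incidence. Definition (2) removes discontinued participants but keeps those already affected. It is therefore neither an increment of cumulative incidence nor a weekly risk among those who can still have a first event.

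This matters because the primary objective is the tolerability of different titration schemes. Protocol 6.1.1 says that the "dose will be titrated over a period of 6 to 10 weeks", and Table 2 there puts 120 mg BID first at Week 7 or 8 (Arms 2 and 1) and 200 mg BID first at Week 11 (Arms 6 and 7). A line that drifts down for arithmetic reasons is lowest in those weeks, and a reader may take the drift for good tolerability at the higher doses.

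**Working it through.** **What the documents give.** There is no planned value for the weekly percentage, so none can be reproduced. The sample size does reproduce: 105/(1 − 0.25) = 140, and (5 × 20 + 15) + (20 + 5) = 140 (Protocol 9.2).

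**Inputs from the documents**
- About 20 participants per active arm and 25% drop-out overall (Protocol 9.2).
- In the 28-day study C3421002, placebo included: nausea 49.0%, vomiting 26.5%, diarrhoea 24.5% of 98 participants, of whom 2 withdrew for adverse events (Protocol 2.2.2.1 and Table 1).

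**Assumptions**
- Constant weekly risk h of a first event, equal for all participants. From 1 − (1 − p)^(1/4), h is 15.5% (nausea), 7.4% (vomiting) and 6.8% (diarrhoea).
- Drop-out spread evenly, 1 − 0.75^(1/12) = 2.37% per week, and unrelated to the event. It then cancels from definition (2).

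**Expected value under definition (2).** In week k it is h(1 − h)^(k−1). The risk among event-free participants stays at h, so the understatement is the factor 1/(1 − h)^(k−1).

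| Event | h | Week 8 shown (factor) | Week 11 shown (factor) |
|---|---|---|---|
| Nausea | 15.5% | 4.8% (3.3) | 2.9% (5.4) |
| Vomiting | 7.4% | 4.3% (1.7) | 3.4% (2.2) |
| Diarrhoea | 6.8% | 4.2% (1.6) | 3.4% (2.0) |

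**Comparison of two arms.** Let Week 1 risk be 40% in one arm and 10% in the other, then 15% per week in both, ignoring drop-out. At Week 8 definition (2) shows 0.6 × 0.85^6 × 0.15 = 3.4% against 0.9 × 0.85^6 × 0.15 = 5.1%. The true Week 8 risk among event-free participants is 15% in both.

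**If affected participants stop IP.** They then leave definition (2) and partly correct it. For h = 15.5%, the Week 12 value by the share of affected participants who stop is:
- 0%: 2.4%
- 4%: 2.5%
- 25%: 3.1%
- 50%: 4.2%
- 100%: 15.5%, the only case with no distortion

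The 4% is the ceiling suggested by C3421002: 2 withdrawals for adverse events against about 48 participants with nausea, 2/48 = 4%. That figure counts study withdrawals, so stopping of IP here could be more frequent; hence the range.

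**A rising risk.** With a true linear rise from 10% to 20% over the 12 weeks, 4% of affected participants stopping and 25% drop-out, the expected line falls from 10.0% to 3.6%.

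**Event-free denominator.** Under the same assumptions a constant risk is shown as constant, and the two arms above both show 15% from Week 2. The number at risk becomes small: for nausea about 20 × 0.845^7 × 0.75^(7/12) = 5.2 at Week 8 and 20 × 0.845^10 × 0.75^(10/12) = 2.9 at Week 11.

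**The case against.** Most of the case on the other side is sound, and it limits the point.

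- **The SAP does not call definition (2) a risk.** It promises a number and a percentage, and the counts and definition (1) stand in the same table. This is true, but the default figure shows only (2), with no caveat.
- **Other outputs answer the clinical questions.** SAP 6.1.1.2.6 plots cumulative incidence of first occurrence with a proper risk set. SAP 6.1.1.2.5 gives weekly prevalence, for which a not-discontinued denominator is suitable. SAP 6.1.1.2.5.1 compares starting doses in Week 1, and SAP 6.1.1.2.2 gives risk differences. The section is labelled exploratory, and no test or decision uses this figure. This stands, and it is why the impact is moderate. A reader might infer that the tolerability assessment as a whole is compromised; the documents do not support that.
- **The nausea factors are the extreme.** A reader might apply them to all three events, but vomiting and diarrhoea give about half as much. The 28-day rates also come from shorter titrations and include placebo.
- **Arm order.** A reader might infer that the arm with worse early tolerability always looks better later, or that the figure reverses the true order. In the example above the later risks are equal, so there is no order to reverse. A true reversal needs later risks that are close.
- **The decline is in expectation only.** With 20 per arm and 10% weekly risk, weekly counts that never rise occurred in about 0.05% of simulated arms.
- **An event-free denominator does not remove selection.** Suppose half an arm has 30% weekly risk and half has none. The event-free percentage still falls from 15% in Week 1 to 0.3 × 0.7^7/(1 + 0.7^7) = 2.3% in Week 8. This stands. The change cures the arithmetic fault but not the loss of susceptible participants, so it needs a footnote.

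**Conclusion.** The point holds as a moderate, cheaply corrected fault in one exploratory table and figure. That definition (2) lacks a clean interpretation follows from the SAP text alone. That it falls in expectation under constant risk holds for any positive risk, unless everyone with the event stops IP.

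The size rests on assumptions: constant weekly risks that are equal across participants, carried forward from a 28-day study. On those, the Week 8 to Week 11 understatement is about 3- to 5-fold for nausea and 1.6- to 2.2-fold for vomiting and diarrhoea. Arms with equal later risk can be shown as different, in favour of the arm with more early events. Definition (1) is sound for its own purpose but should not be read as weekly risk either.

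**What to change.** In SAP 6.1.1.2.4, for the table and the default figure:

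- Use as denominator the participants who, before the week in question, had discontinued neither IP nor the study and had no post-dose occurrence of that event.
- Keep definition (1) in the table. Definition (2) may stay there if footnoted as not being a risk among event-free participants.
- Print the number at risk under each week.
- Add a footnote that late-week values rest on few participants. It should also say that those still event-free may be less susceptible, so a fall over the weeks is not by itself evidence of better tolerability at higher doses.

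The cost is one changed sentence, the footnotes and one changed denominator in a program. The downside is noise: with about 3 at risk in Week 11 in the nausea-like case, a single event plots as roughly 30%, and the obesity placebo group starts with only about 5 participants.
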